4.5.1. Primary Objective

• To test the effect of a sequential treatment approach consisting of SPS/SPS and SPS/CBCM on functioning levels of UHR patients 6 months post baseline (end of Step 2), as measured using the Global Functioning: Social and Role Scales (138).

4.5.2. Secondary Objectives

- To test the effect of a sequential treatment approach consisting of SPS, CBCM and antidepressant medication on functioning levels of UHR patients 12 months from baseline (end of Step 3), as measured using the Global Functioning: Social and Role Scales.
- To test effect of a sequential treatment approach consisting of SPS, CBCM and antidepressant medication on transition to psychotic disorder by 12 months and 24 months from baseline, as assessed using the CAARMS (142).
- To test the effect of a sequential treatment approach on UHR status (maintenance versus remission) 1.5 months, 6 months, 12 and 24 months from baseline.
- To test the effect of a sequential treatment approach in UHR patients on level of psychiatric symptomatology, including positive psychotic symptoms, negative psychotic symptoms and depressive symptoms 6 months, 12 months and 24 months from baseline.
- To test relapse rates (to UHR+ status) in the relapse prevention/responder arm of the trial (SPS v monitoring) during the first 12 months.

4.5.3. Exploratory Objectives

The study aims to also explore whether there is a relationship between treatment response and specific patient profiles. In the subset of responders to a specific intervention, such as

- 638 CBCM or antidepressants, the study will examine whether it is likely that the treatment was 639 effective due to the proposed putative mechanisms (cognitive biases and neuroprotection).
- We will measure psychological variables at baseline, entry and exit from steps two and three and inflammatory, neuroendocrine and oxidative stress-related biomarkers, as well as antibodies to infectious agents and complement proteins at baseline, entry and exit from step three to test whether these variables moderate or mediate response to treatment.

It is expected that responders to CBCM will be those with more prominent cognitive biases and vulnerabilities at baseline, and which would improve in response to CBCM. The study will also investigate whether response to SPS or CBCM in Step 2 is mediate/moderated by degree of therapeutic alliance (quality of therapeutic relationship) between the participant and clinician. The study will also investigate whether CBCM and SSRIs have any impact on inflammatory and/or neuroendocrine, antibodies to infectious agents, complement proteins and oxidative stress biomarkers. Based on the background material reviewed above, we will also examine whether neurocognition, CSF complement proteins and genetic variables predict outcome (persistent attenuated psychotic symptoms, transition to psychosis, poor functioning) and moderate/mediate response to treatment. Since schizophrenia/psychosis and other deleterious clinical and/or functional outcomes (e.g., persistent severe mood and anxiety disorders) have a biological basis, in addition to psychosocial contributing factors, thorough investigation of potential biomarkers, informed by recent major breakthrough scientific findings (127) using cutting edge technologies, is highly warranted in a study of the present scope and scale. In the parents' study, we will also aim to explore the parent's experience of their child being identified to be at-risk for a major mental illness and their appreciation of autonomy in young people's risk identification and interventions. We will also explore their understanding of the balance between beneficence, risks and autonomy in the different STEP interventions and their preferences for future interventions.

662663

664

665 666

667

668 669

670 671

672

644

645

646

647

648

649 650

651

652

653

654

655

656 657

658

659

660

661

[figure not shown]
5. Study Design

6.1 Description

This is a sequential multiple assignment randomized trial (SMART). Clients who are classified as being non-responders at the end of a Step will graduate to the next stage of intervention, while responders are offered entry to a maintenance/relapse prevention arm in which modest psychosocial care is compared in a randomised design with monitoring alone throughout the first 12 months of the study. A "fast fail" feature is included in step 3 if the participant deteriorates or fails to show improvement. This consists of dose enhancement and entry to a personal choice/shared decision-making treatment option.

Research Assistants conducting the clinical assessments will be blind to treatment allocation (Steps 2: single-blind). Step 3 of the study incorporates a randomised, double-blind, placebo-controlled stage of the study. Both participants and the study team will be blind to treatment (SSRI/placebo). The full study design is represented in Figure 1.

678 Figure 1. Study Design

679 **Notes.**

677

680

686

687

689

690

691 692 **SPS** = Support and Problem Solving.

CBCM = Cognitive Behavioural Case Management.

SSRI = Selective Serotonin Reuptake Inhibitor.

Rescue: At all stages, participants whose psychotic symptoms worsen to full threshold psychosis or who develop acute mania or sustained aggressive or suicidal risk will be discontinued from study treatment and treated according to clinician's choice, typically with antipsychotic or antidepressant medication.

Responders: Participants who no longer meet UHR criteria at the end of an intervention stage, as well as on at least one other assessment point, and an improvement of ≥ 5 points on the SOFAS or a SOFAS score of ≥ 70 .

688 The design consists of 3 steps:

Step 1: Open-label Support & Problem Solving (SPS): "Open-label" SPS will be provided to all participants. Owing to the inherent difficulties associated with engaging this client group, there is no minimum number of sessions of SPS. Instead the SPS will be delivered as clinically indicated and practically possible within the 6-week period. We expect this initial

step will produce resolution of the current clinical phenotype in around 50% of participants, and thereby enrich the remaining sample for psychosis risk and functional impairment for randomisation in subsequent steps (57, 58). We also expect this to help retention of participants as drop outs have tended to occur early in previous UHR trials (93). Participants who respond to Step 1 (see below for definition of response) will be randomised to SPS monthly sessions v Monitoring at 3, 6, 9 and 12 months post entry to Step 1.

Monitoring will consist of the research assistant conducting a research assessment in addition to the clinician making contact with the participant, either by phone or in person, in order to monitor mental state and risk and to assess whether there has been any mental health deterioration which would indicate a need for change in clinical management (e.g., referral to a new service or need to re-engage with headspace or Orygen).

Step 2: CBCM vs SPS: Participants who do not respond (estimated at 50%) to Step 1 will be randomised to one of two treatment groups for 18 weeks (4.5 months): A more intensive psychosocial intervention (cognitive behavioural case management: CBCM) versus SPS. This design will test the potential benefit of a more intensive psychosocial intervention compared to extending the more basic intervention provided in Step 1 (SPS). It is not yet clear whether CBT, the primary component of CBCM, offers benefits over and above SPS. It is possible that non-responders to Step 1 (6 weeks of SPS) have simply not received the SPS intervention for long enough (i.e., the "dose" of SPS has not been sufficient to achieve symptom response and functional improvement). Extending SPS to a total of 6 months duration in Step 2 will test this possibility, as well as the potential benefit of introducing a more intensive psychotherapy in the form of CBCM. Research assistants conducting the research assessments will be blind to treatment allocation. This step will test an intervention that targets a key putative mechanism for psychosis vulnerability and risk: the psychological mechanism of dysfunctional cognitive biases.

Step 3 CBCM + SSRIs vs CBCM + Placebo: The estimated 50% who do not respond by the end of Step 2 (27, 56) will be randomised to antidepressant medication (fluoxetine: initial dose 20mg/day) or placebo, in addition to CBCM, for a further 6-month period. Randomisation will be stratified based on depression scores (MADRS total score <21 or ≥21). Previous UHR data at our service indicates that approximately half of recruited patients will score ≥21 on the MADRS. This stage will test whether antidepressant medication in addition to CBCM contributes to improving the outcome of those who have failed to respond to previous interventions. This stage of the study incorporates a randomised, double-blind approach with both the participants and study teams members being blinded to treatment allocation. Antidepressants have previously shown potential but not conclusive benefits for UHR patients. The dose of SSRI will be titrated up at 6 weeks from 20 mg to 40 mg daily (one to two capsules of matching placebo) if there is no response based on clinical judgment of the

730 treating doctor. It is appropriate to reserve antidepressants for this third step in view of their 731 higher risk of adverse effects. They may be effective either immediately or in terms of risk 732 reduction for psychosis or other non-psychotic syndromes via an effect on depression or 733 anxiety or via a neuroprotective route (140). By stratifying by depression at this stage of 734 randomisation, we will be able to determine the impact of antidepressant medication on 735 outcome in this population in relation to intensity of depressive symptoms, which will have 736 direct implications for clinical decision-making as well as shed light on the possible 737 mechanisms underlying the benefit of antidepressant medication for this patient group (i.e.,

- as neuroprotective or an indirect pathway via improvement of mood disturbance).
- "Fast fail" in Step 3: Step 3 will incorporate a "fast fail" feature such that if patients
 deteriorate or have not responded after 12 weeks of this third step of the study, they will be
 offered the option of:
- 742 1. Continuing as randomised.

748749

750

751752

753

754

755

756

757

758

759

760

761

762

763

764

765

- 743 2. Increasing the dosage of antidepressant medication/placebo to 40mg if this has not already been done.
- Continuing the antidepressant or placebo with the addition of Omega-3 fatty acids or
 low dose antipsychotic medication chosen via a shared decision making approach,
 supported by accessible information on the pros and cons of this decision.

Non-responders: All participants who do not meet the 'response' criteria below (and who have not yet made a transition to first episode psychosis or mania).

Responders: All responders during Steps 1 and 2 will be randomized at the end of each step to monthly SPS sessions or simple monitoring at 3 monthly intervals (Response to Step 1; 6, 9 and 12 months; Response to Step 2: 9 and 12 months) to assess whether such responses can be sustained. All relapsing participants at any stage and all non-responders at the 12 month point will be reassessed and offered "treatment as usual" via headspace and Orygen. In year 2 all participants will be clinically monitored and receive research follow up at 6-month intervals (18 and 24 months).

Rescue: Finally, a safety net or "rescue" strategy is built into the study design from Step 1 through to the end of Step 3 where participants whose psychotic symptoms worsen to the point of full threshold psychosis, or who develop acute mania, or sustained aggressive or suicidal risk as defined using the CAARMS are discontinued from study treatment and treated according to clinician's choice, typically with antipsychotic or antidepressant medication, either as inpatients or with intensive community care and with full evidence-based psychosocial care (see Section 7.8).

767

768

769

770

771

772

773

774

775

776

777

778

779

780

- Moderators and mediators of response: In addition to testing the efficacy of the treatments in Steps 2 and 3 we will be exploring as a secondary aim whether there is a relationship between response and specific forms of treatment. Hence in the responders to a specific intervention such as CBCM or antidepressants, we will address whether the treatment is likely to be working through the putative mechanism proposed. We will measure psychological variables, inflammatory and oxidative stress, antibodies to infectious agents, complement proteins and immunoglobins, and related biomarkers at baseline, entry and exit from steps two and three. We expect that responders to CBT will be those with more prominent cognitive biases and vulnerabilities at baseline, and which would improve in responders to CBT. We will also examine: i) whether CBCM has any impact on inflammatory and/or oxidative stress biomarkers, as well as antibodies to infectious agents, complement proteins and immunoglobins, ii) whether neurocognition and genetic variables predict outcome (persistent attenuated psychotic symptoms, transition to psychosis, poor functioning) and moderate/mediate response to treatment (e.g., whether COMT Val158Met polymorphism influences CBCM response).
- 781 **Response:** The definition of response is as follow:
- The Global Rating Scale or the Frequency score need to be less than 3 for all of the four
 positive symptoms (UTC, NBI, PA and DS) and
- There is an improvement of at least 5 points in SOFAS compared with baseline or the SOFAS score is at least 70.
- The response status will be determined using the "current" ratings of CAARMS and will be determined at weeks 4, 6, 12, 24, 36, 52. These current ratings are based on the patients' experience in 'the last fortnight' and are for the four positive symptoms only.
- 789 The definitions for a responder at the different time points are as follow:
- A responder at the end of Step 1 is one who shows a response at both weeks 4 and 6.
- A responder at the end of Step 2 is one who shows a response at both weeks 12 and 24.
- A responder at week 36 is one who shows a response at week 36 this is for the fast fail
 option.
- 794 Key:
- 795 UTC = Unusual Thought Content subscale of the CAARMS
- 796 NBI = Non-Bizarre Ideas subscale of the CAARMS
- 797 PA = Perceptual Abnormalities subscale of the CAARMS
- 798 DS = Disorganised Speech subscale of the CAARMS
- 799 SOFAS = Social and Occupational Functioning Assessment Scale
- 800 Non-response: All participants who do not meet the 'response' criteria (and who have not
- yet made a transition to psychosis or mania).

All participants will be closely monitored for adverse events and concomitant medication use throughout the study. Vital sign measurements, and clinical laboratory evaluations will be performed at predefined time points throughout the study as shown in the Schedule of Assessments in Section 4.

806 807

808 809

810

811

812

813

814

815

829 830

802

803

804 805

Parents' sub study (EXPECT): We propose to conduct 25 interviews with parents of young people (12-18 yrs) who have already consented to STEP. After full informed consent (and assent from young people), the researchers will gather specific information from parents with semi-structured interview prompts Information about probability of risk is assessed using prompts from the semi-structured interview developed by Erickson and colleagues (2014) (162). Interviews will be conducted by two trained medical students under the supervision of [name] and [name]. The study is expected to be conducted between Feb and May 2019.

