5.2. Study Endpoints

5.2.1. Primary Endpoint

The primary endpoint is 6 months post-baseline (end of Step 2). The study will test the effect of the sequential treatment approach of SPS and CBCM on functioning levels at this time point. Functioning will be measured using the Global Functioning: Social and Role Scales (135).

837

835 **5.2.2. Secondary Endpoint(s)**

- Functioning levels 12 months from baseline (end of Step 3), as measured using the Global Functioning: Social and Role Scales.
- Transition to psychotic disorder by 12 months and 24 months from baseline, as assessed using the CAARMS (142).
- UHR status (maintenance versus remission) 1.5 months, 6 months, 12 and 24 months into treatment as determined by the CAARMS.
- Psychiatric symptomatology, including positive psychotic symptoms, negative psychotic
 symptoms and depressive symptoms 1.5 months, 6 months, 12 months and 24 months
 into treatment assessed using the CAARMS, BPRS, SANS and MADRS.
- Relapse rates (i.e., relapse to UHR+ status) in the relapse prevention/responder arm of the trial (SPS v monitoring) during the first 12 months.

847 **5.3. Study Duration**

- The controlled intervention component of the study is of 12 months duration. Participants
- will be followed up with research assessments up to 24 months post-baseline.

850 **5.4. Study Risk Assessment**

- Participants in the active treatment arm of the study will have regular (ideally weekly-
- 852 fortnightly) contact with their treating team (case managers and/or psychiatrist), during
- 853 which risk will be monitored. Participants in the non-active treatment arm will either have
- 854 monthly contact with their treating team or undergo 3-monthly monitoring. If participants
- are deemed to be at substantial risk to themselves or others (see definition in 9.8.2) they will
- 856 be discontinued from the study and receive required clinical care. These participants will
- continue to be followed up with research assessments.

6. Participant Population

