A participant will be considered eligible for inclusion in this study only if all of the following criteria apply:

- 1. Age 12 25 years (inclusive) at entry
- 2. Ability to speak adequate English (for assessment purposes)
- 3. Ability to provide informed consent. Where participants are minors (i.e. have not reached the age of eighteen), consent will also be obtained from one of the participant's parents or legal guardian. Both the parent/legal guardian and participant will be required to sign a consent form in such a case. It will be the treating doctor's decision made in consultation with the investigator to determine whether a participant who is a mature minor has the capacity and competence to consent to the study.
- 4. Meeting one or more UHR for psychosis groups (as defined in Table 1).

902 Young people seeking help via headspace centres are routinely screened using the HEADSS

assessment, and as clinically appropriate, an additional screening tool will be used by clinicians which will help them determine the UHR status of their clients. This tool is the Prodromal Questionnaire-16 (PQ-16)(144). Those who score 6 or more positive symptoms on the PQ-16 will be assessed using the CAARMS(142) and SOFAS(148) to determine UHR status. A cut-off score of 6 on the PQ-16 screening tool has previously been found to identify UHR+ cases with high sensitivity (87%) and specificity (87%) (144) and has also been found to identify a more enriched sample for psychosis risk (146). This will not apply at the PACE clinic as all clients have already been assessed as UHR + through clinician administered CAARMS (as part of standard clinical entry).

Table 1: Operationalised UHR intake criteria

913 914

903

904

905 906

907

908 909

910

911

912

1. Group 1: Vulnerability Group

Family history of psychosis in first degree relative OR Schizotypal Personality Disorder (as defined by DSM IV) in identified patient

AND

Drop in Functioning:

Recency: Change in functioning occurred within last year

Impact: SOFAS score at least 30% below previous level of functioning and sustained for at least one month.

OR

Sustained low functioning:

Recency: For the past 12 months or longer

Impact: SOFAS score of 50 or less.

915 916

2. Group 2: Attenuated Psychotic Symptoms Group

2a) Subthreshold intensity:

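### The protocol defines responder in two ways, and the detailed rule lets a participant who entered only through Group 1 count as a responder while still meeting the UHR entry criterion

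*Protocol*

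**What the plan says.** **Entry.** Section 6.5 requires "Meeting one or more UHR for psychosis groups (as defined in Table 1"), so one group is enough. Group 1 needs a trait, "Family history of psychosis in first degree relative" or schizotypal personality disorder, together with one of two functional conditions:
- drop route: "SOFAS score at least 30% below previous level of functioning and sustained for at least one month", with the change falling within the last year;
- sustained-low route: "SOFAS score of 50 or less" for 12 months or longer.

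Neither route asks for a CAARMS positive-symptom score.

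**Response, detailed rule** (Study Design, Description, Response paragraph). The symptom part reads: "The Global Rating Scale or the Frequency score need to be less than 3 for all of the four" positive symptoms, rated on the last fortnight. The functional part reads: "There is an improvement of at least 5 points in SOFAS compared with baseline", or a SOFAS score of at least 70. Step 1 response must be shown at weeks 4 and 6, and Step 2 response at weeks 12 and 24. The Non-responders paragraph in the same section points forward to these criteria.

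**Response, Figure 1 note** (same section). A responder must have ceased to meet UHR criteria at the end of the stage and at one further assessment, and must also meet the SOFAS condition. Section 6.2 takes the same view: it equates those still UHR+ at six weeks with non-responders to Step 1.

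**Use.** Responders are randomised to monthly SPS or monitoring. The endpoint in Section 5.2.2 is "Relapse rates (i.e., relapse to UHR+ status") during the first 12 months, and Hypothesis 4 tests it.

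**The concern.** Two definitions of one routing variable are in force, and they disagree about a recognisable kind of participant. For someone admitted on symptoms (Groups 2 and 3), the symptom part of the detailed rule at least tests the feature that brought them in. For someone admitted only through Group 1, that part may be satisfied on Day 1. The functional part then tests change from baseline, not departure from the entry range. Such a person can be a responder under the detailed rule and a non-responder under the Figure 1 note.

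Two analyses are exposed. The Step 1 response rate (Hypothesis 1) would count people who are still UHR+. In the SPS versus monitoring comparison (Hypothesis 4), the event for these people is either already present at randomisation or cannot be defined. If they are counted as relapsed, they add events that treatment cannot influence, in both arms, and pull the comparison towards no difference.

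**Working it through.** The protocol gives no figure to reproduce on this point. The check applies the stated thresholds and then makes an illustrative estimate of size.

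**1. Symptom part at baseline.** A Group 1-only entrant scoring 0 on all four CAARMS positive subscales is outside Group 2 and Group 3, and has every rating below 3. The symptom part is met before any treatment.

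**2. Sustained-low route.** The entry range is SOFAS of 50 or less. With baseline B and a rise of exactly 5, the participant stays in range if B + 5 ≤ 50, that is B ≤ 45. So 45 to 50 remains in Group 1, and 46 to 51 does not.
*Example:* SOFAS 42 for 18 months, then 47 at week 4 and 48 at week 6. The rises are 5 and 6, so the detailed rule gives a responder. SOFAS is still 50 or less and has been for over 12 months, so Group 1 is still met.

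**3. Drop route.** The ceiling is 0.70 × previous level P. After a rise of 5 the participant is still in Group 1 if B ≤ 0.70P − 5.

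| Previous level P | Ceiling 0.70P | Still in Group 1 after +5 if B is at most |
|---|---|---|
| 60 | 42 | 37 |
| 70 | 49 | 44 |
| 80 | 56 | 51 |
| 90 | 63 | 58 |
| 100 | 70 | 65 |

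*Example:* P = 80 and B = 48, which is 40% below. Weeks 4 and 6 are 54 and 55: rises of 6 and 7, so a responder. Both are under the ceiling of 56 (32.5% and 31.25% below), so Group 1 is still met.

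**4. The two definitions applied.** Both examples are responders under the detailed rule. Neither is under the Figure 1 note, because UHR criteria are still met.

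**5. Size, by simulation on assumed inputs.** True SOFAS has mean 48 and SD 6. Visit error is independent with SD 3 to 6. Entry requires an observed baseline of 50 or less, and there is no true change. Response is a score at least 5 above baseline at both weeks 4 and 6. There were 400,000 draws per setting. Only the sustained-low route was simulated.

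| Visit error SD | Respond by chance | Of these, still ≤ 50 at both visits | Product |
|---|---|---|---|
| 3 | 5.9% | 46.7% | 2.8% |
| 4 | 11.6% | 41.3% | 4.8% |
| 5 | 17.0% | 36.8% | 6.3% |
| 6 | 21.4% | 32.9% | 7.0% |

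If 5% to 20% of the 500 participants entered through Group 1 only (25 to 100 people, assumed) and all are treated like the simulated route:
- lowest: 25 × 0.059 × 0.467 = 0.7;
- highest: 100 × 0.214 × 0.329 = 7.0.

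That is about 1 to 7 people. Against the 250 Step 1 responders implied by Hypothesis 1 (50% of 500), it is 0.7/250 = 0.3% to 7.0/250 = 2.8%. Small true gains that stay inside the entry range would add to this and are not quantified.

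**6. What dilution would look like.** Assume 100 per arm and true relapse of 40% versus 25%. If a share g of both arms is already UHR+ and counted as relapsed, the rates become g + (1 − g) × 0.40 and g + (1 − g) × 0.25. Power is 62% at g = 0, 56% at g = 5%, 50% at g = 10% and 40% at g = 20%. Even the smallest non-zero g shown exceeds the chance-only range in step 5, so these losses mark direction and not an expected size.

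**The case against.** The strongest reply is that the Figure 1 note already closes the gap: under it, neither example is a responder. A reader might infer that nothing in the protocol requires UHR status to be lost, and the note shows that inference to be wrong. The note does not settle the matter, though. The Non-responders paragraph points to the detailed rule, and neither text is said to supersede the other. What remains is a contradiction, not a simple omission.

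Other points on that side:
- **The functional part does speak to Group 1.** The trait cannot be expected to remit in six weeks, and SOFAS is the other half of the criterion. This is fair. The difficulty is only that a 5-point change need not carry a participant out of the entry range.
- **Screening may make such entrants rare.** At headspace sites those scoring 6 or more on the PQ-16 go on to CAARMS and SOFAS. The exempt PACE clinic sees about 100 UHR cases a year, against about 2000 eligible at headspace. This stands as a limit on size. It does not exclude the case, because a self-report screen and a CAARMS rating can differ.
- **How relapse is operationalised may sit in the SAP**, which is not at hand. That is possible, but the contradiction over who is a responder lies within the protocol itself.
- **The primary result is safe.** A reader might infer that the SPS versus CBCM comparison is biased. The documents do not support that: it is randomised among those classed as non-responders and uses the Global Functioning: Social and Role Scales. Only the make-up of the Step 2 sample changes, not the balance of its arms.

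**Conclusion.** The point holds as a contradiction between two responder definitions, with a definite consequence for Group 1-only entrants under the detailed rule. That the detailed rule permits a responder who still meets Table 1 follows from the stated thresholds alone. That relapse is then already true at time zero also assumes that UHR+ means meeting any Table 1 group; the protocol states no narrower meaning for this endpoint.

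The size is unknown because the Group 1-only share is not given. On the assumed inputs, about 1 to 7 people would be chance responders still in the entry range. A reader might instead take all chance responders as affected, which would be 25 × 5.9% = 1.5 up to 100 × 21.4% = 21. That is too many for this point, since it includes people whose SOFAS has risen above 50 and who have left the range. The SOFAS mean, its SD and the visit error are all assumptions.

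The analyses affected are the Step 1 response rate and the SPS versus monitoring relapse comparison. This merits correction, but it does not threaten the primary analysis.

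**What to change.** 1. Reconcile the Figure 1 note, the Response paragraph and the wording in Section 6.2 so that one definition of responder applies. Because response status decides which treatment follows, the routing consequence is for the sponsor to settle.
2. State whether UHR+ in the relapse endpoint includes Group 1, and how relapse is counted for someone who met Group 1 when randomised as a responder.
3. Report Step 1 response (Hypothesis 1) and the SPS versus monitoring relapse comparison (Hypothesis 4) with and without Group 1-only responders who still met Table 1 at that randomisation. Their status is fixed before allocation, so leaving them out keeps the comparison randomised.

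The third item is the practical one. Version 10 is dated October 2020 and the last visit is planned for January 2021. With 24 months of follow-up per participant, the last entry would be around January 2019, so the Step 1 and Step 2 responder allocations have been made.

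**Cost:** a few sentences of text, one sensitivity analysis from SOFAS and intake-group data already collected, and a slightly lower response rate when these participants are not counted.
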